#### 11.4.2.2 Contrast Sensitivity

Mean photopic (with glare) and mesopic (with and without glare) contrast sensitivity at Post-Operative Visit 4 will be summarized using continuous summary statistics by lighting condition, spatial frequency, treatment group, and visit.

### 11.4.3 Primary Performance Analyses

#### 11.4.3.1 Photopic Monocular UDVA

Photopic monocular uncorrected distance visual acuity (UDVA) at 4 m in first implanted eyes at Post-Operative Visit 4 will be summarized in logMAR units using continuous summary statistics by treatment group for the PP Set. Imputation of missing data is not conservative in non-inferiority testing. Therefore, missing data will not be imputed for the UDVA non-inferiority test. The treatment effect (mean Test [enVista trifocal] group IOL VA minus mean Control [enVista monofocal] group IOL VA) in logMAR units will be estimated in addition to a two-sided 90% confidence interval, using a statistical model with treatment and site as fixed factors. If the upper confidence limit (equivalent to a one-sided upper 95% confidence limit for the treatment effect) is less than 0.2 logMAR, then the Test enVista trifocal lens will be statistically non-inferior to the control enVista monofocal lens.

The previous continuous summary statistics will also be provided for the ITT Set. However, statistical success will not depend upon the results of the ITT analysis.

# 11.4.3.2 Photopic Monocular UNVA

Photopic monocular uncorrected near visual acuity (UNVA) at 40 cm at Post-Operative Visit 4 (Day 120 to Day 180 after second eye IOL implantation) will be summarized using continuous summary statistics in logMAR units by treatment assignment for the first implanted eyes of ITT Set Subjects.

If there are missing ITT analysis set monocular UNVA values at Visit 4, then missing data will be imputed using the Markov chain Monte Carlo (MCMC) multiple imputation method. After imputation of missing data, the statistical hypotheses will be tested using statistical models with treatment and site as fixed factors by imputation.

An overall p-value resulting from the multiple imputation method will be estimated. The treatment effect (mean Test group IOL VA minus mean Control group IOL VA) in logMAR units will be summarized using continuous summary statistics and a two-sided 95% confidence interval. If the p-value from the multiple imputation analysis is less than or equal to 0.05 and the treatment effect is less than zero (i.e., the Test lens mean logMAR VA is superior to the mean for the control), then it will be concluded that the Test IOL is statistically successful (i.e., superior to the Control IOL) in this outcome.

The previous continuous summary statistics will also be provided for the Per Protocol Set. However, statistical success will not depend upon the results of the PP analysis.

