An anticipated benefit which a subject may derive from participation in this study is an improvement of their vision as a result of the removal of their cataracts. If the subject is randomized to receive the enVista MX60E monofocal IOL, it is expected they will have improvement in their distance vision and would then require the use of corrective lenses (such as glasses or contact lenses) for near and intermediate vision. If a subject is randomized to receive the enVista MX60EFH trifocal IOL, they may have improvement in their near and intermediate vision while maintaining comparable distance visual acuity to a monofocal IOL, allowing them to be able to read, use a computer, and watch television without reading glasses or bifocals.

Further discussion of potential or actual risks during cataract surgery and with the use of multifocal or monofocal enVista IOLs as well as IOL injectors to be used in this study can also be found and should be accessed in the study Investigator's Brochure and/or the relevant IOL Directions for Use (DFU) provided by the Sponsor as manufacturer. Of note, the enVista IOL medical devices according to the Design Risk Analysis (DRA) are not susceptible to environmental influences or concomitant medical treatments once implanted in a patient's eye.

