#### 11.2.1.2 UNVA

A two-group t-test with a 5% two-sided significance level will have > 99% power to detect a difference in means of 0.2, assuming that the common standard deviation is 0.15, when the sample sizes in the two groups are 100 and 50, respectively (a total sample size of 150).

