# 11.4.3.3 Photopic Monocular UIVA

Photopic monocular uncorrected intermediate visual acuity (UIVA) at 66 cm in first implanted eyes will be summarized and analyzed using the methods described for UNVA.

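### The primary acuity models leave the variance structure unstated; with 2:1 allocation, a single pooled variance gives valid error rates and intervals only if both arms have the same SD

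*Combined protocol and SAP*

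**What the plan says.** Section 11.4.3.2 (UNVA) states that, after multiple imputation, "the statistical hypotheses will be tested using statistical models with treatment and site as fixed factors by imputation". The results are combined into one p-value and a two-sided 95% interval. The success rule reads: "If the p-value from the multiple imputation analysis is less than or equal to 0.05 and the treatment effect is less than zero". Section 11.4.3.3 says that UIVA "will be summarized and analyzed using the methods described for UNVA". Section 11.4.3.1 estimates the UDVA difference "using a statistical model with treatment and site as fixed factors" and compares the upper limit of a two-sided 90% interval with 0.2 logMAR.

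None of these sections says whether the residual variance is shared or arm-specific, and none mentions a robust standard error or a degrees-of-freedom method. The synopsis names two-sample t-tests for UNVA and UIVA, without a site term and without saying whether they pool the variance.

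The documents' only statement about the spread of acuity is in the sample-size sections. For UNVA, Section 11.2.1.2 claims power above 99% for a 0.2 logMAR benefit on this premise: "assuming that the common standard deviation is 0.15, when the sample sizes in the two groups are 100 and 50". Sections 11.2.1.1 (UDVA) and 11.2.1.3 (UIVA) use the same SD. Section 7.1 sets the 2:1 allocation, which makes Control the smaller arm.

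**The concern.** With equal group sizes, a pooled variance does little harm when the SDs differ. With 2:1 allocation that protection is lost. The pooled estimate is dominated by the larger arm, while the uncertainty of the difference is dominated by the smaller one. If the smaller arm is the more variable, the standard error is too small; if it is the less variable, the standard error is too large.

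There is a reason to doubt equal SDs at 40 and 66 cm. The trifocal has add powers for those distances, whereas Section 10.3 expects that Control subjects "would then require the use of corrective lenses (such as glasses or contact lenses) for near and intermediate vision". Uncorrected acuity in an eye that is out of focus may depend more on residual refraction and pupil size. That makes a larger Control SD plausible, but it does not establish one.

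At stake are the error rate of three primary tests and the 95% intervals that will be reported as the size of the near and intermediate benefit.

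**Working it through.** **Inputs.** 100 Test and 50 Control eyes, SD 0.15, difference 0.2, two-sided 5% (Sections 11.2.1.2 and 11.2.1.3); about 12 sites (Section 5.2). The Control/Test SD ratio r is not in the documents and is varied here as an assumption.

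**1. The plan's own figures.** SE = 0.15 × √(1/100 + 1/50) = 0.0260, and 0.2/0.0260 = 7.70. Against a critical value of 1.976 (148 df), power exceeds 0.9999, so the stated >99% reproduces. The enrolment figures do too: 100/0.9 = 111.1, rounded up to 112, and 50/0.9 = 55.6, rounded up to 56.

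**2. Pooled against true standard error.** With the Test SD set to 1 and the Control SD to r:

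- pooled SE² = [(99 + 49r²)/148] × 0.03
- true SE² = 1/100 + r²/50
- k = pooled SE / true SE
- two-sided size ≈ 2[1 − Φ(1.976k)]

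At r = 1.5, pooled SE² = (209.25/148) × 0.03 = 0.04242 and true SE² = 0.055. So k = √(0.04242/0.055) = 0.878, and size ≈ 2[1 − Φ(1.735)] = 8.3%.

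**3. Results over the assumed range.** The simulated columns come from 40,000 trials per ratio: a least-squares fit with treatment and 12 site effects, normal data, no true difference and no missing data. Coverage is 100% minus the closed-form size.

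| r (Control/Test SD) | k | Size, closed form | Size, simulated | Favouring Test, simulated | 95% CI coverage |
|---|---|---|---|---|---|
| 0.67 | 1.137 | 2.5% | 2.7% | 1.3% | 97.5% |
| 0.8 | 1.077 | 3.3% | – | – | 96.7% |
| 1 | 1.000 | 4.8% | 4.8% | 2.4% | 95.2% |
| 1.1 | 0.969 | 5.6% | – | – | 94.4% |
| 1.25 | 0.929 | 6.6% | 6.8% | 3.3% | 93.4% |
| 1.5 | 0.878 | 8.3% | 8.7% | 4.4% | 91.7% |
| 2 | 0.815 | 10.7% | 11.1% | 5.4% | 89.3% |

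The closed form uses a normal tail and runs slightly low. A simulated pooled t-test without site gives 2.6%, 3.5%, 6.9%, 8.5% and 11.1% at r = 0.67, 0.8, 1.25, 1.5 and 2, so the site term makes little difference.

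**4. Methods that allow unequal variances.** For r from 1 to 2, the simulated size is 4.8–5.1% for Welch's test. In the site model it is 4.9–5.6% with HC2 and 4.0–4.5% with HC3 standard errors.

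**5. Interval width and power, Test SD 0.15.**

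- Control SD 0.225: pooled half-width 1.976 × 0.0309 = 0.061; unequal-variance half-width 1.994 × 0.0352 = 0.070.
- Control SD 0.30: pooled 1.976 × 0.0367 = 0.0725; unequal-variance 1.999 × 0.0450 = 0.090.
- Unequal-variance power at a difference of 0.2 is 0.9999 and 0.992 respectively.

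**6. UDVA.** The one-sided 5% error at the margin is roughly 6.3%, 7.5% and 9% at r = 1.25, 1.5 and 2. At an observed difference of zero with SDs 0.15 and 0.30, the unequal-variance upper limit is about 1.67 × 0.045 = 0.075, well below 0.2.

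**The case against.** The strongest reply is that the plan never says it pools. A reader might infer from the shared planning SD that the analysis assumes equal variances. The documents do not support that: a sample-size assumption does not define the analysis model, and a model with fixed effects for treatment and site can carry arm-specific variances. Section 11.4 also defers further detail to a SAP approved before database lock. All of this stands. The accurate finding is that the variance structure is unstated and that the ordinary fit pools.

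A reader might also infer that these tests will run at 7–11%. That needs an SD ratio of about 1.25 to 2, which nothing in the documents establishes. Section 10.3 speaks to the level of near and intermediate vision without correction, not to its spread. Residual refraction and pupil size can affect a diffractive, apodized trifocal too, and the limit on corneal astigmatism (exclusion criterion 15) narrows refractive spread in both arms. If Test is the more variable arm, the error is on the safe side.

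Nor is 7–11% the chance of a false claim. Success also requires an effect below zero, so rejections favouring Control do not count, and Section 11.4 requires every primary endpoint with a success criterion to be met.

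Finally, at the planned effects no decision changes, and the simulations left out multiple imputation, so exact rates for the planned analysis are untested.

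These points limit the size of the concern but do not remove it. Because the direction is unknown, the better choice is a method that is valid either way. Deferral to the SAP only says where the sentence belongs.

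**Conclusion.** The point holds as a free improvement, not as an error that threatens the trial's conclusion. If the models are fitted with one residual variance, the 100/50 split makes their standard errors depend on equal SDs.

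Under an assumed Control/Test ratio of 1.25, 1.5 or 2, two-sided size is about 6.8%, 8.5% or 11%, and false success for Test on a single superiority endpoint is about 3.3%, 4.4% or 5.4% against 2.5%. Coverage is about 93%, 91.5% or 89%. At a ratio of 1.1 the size is only about 5.6%. At 0.8 or 0.67 it falls to about 3.5% or 2.6%, with intervals that are too wide.

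These figures assume normal data, 100/50 evaluable eyes and no imputation. Superiority at a true 0.2 difference is not in doubt under either method. What changes is the validity of the error rate and the interval: for example, a 95% half-width of 0.070 rather than 0.061 logMAR at SDs of 0.15 and 0.225.

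**What to change.** In Sections 11.4.3.1 to 11.4.3.3, or in the SAP before database lock, keep the fixed effects for treatment and site. Add that the residual variance is estimated separately for each treatment group, with Satterthwaite or Kenward-Roger degrees of freedom; heteroscedasticity-robust standard errors are an acceptable alternative. Apply this to UDVA, UNVA and UIVA. For UNVA and UIVA, combine over imputations as already planned, and check that the imputation model does not itself force one variance on both arms. Replace the synopsis two-sample t-test with the same model.

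The cost is a sentence and a model option, with no extra subjects or data. If the SDs are in fact equal at 0.15, the two-group calculation gives a half-width of 0.0516 instead of 0.0513, and power stays above 99%.

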### Primary Performance Analyses

Photopic monocular logMAR UDVA at Post-Operative Visit 4 will be summarized using continuous summary statistics by treatment group for first eyes of the Per Protocol (PP) Set. Imputation of missing data is not conservative in non-inferiority testing. Therefore, missing data will not be imputed for a UDVA non-inferiority test. The treatment effect (mean Test group IOL visual acuity minus mean Control group IOL visual acuity) in logMAR units will be estimated in addition to a one-sided upper 95% confidence limit. If the upper confidence limit for the treatment effect is less than 0.2 logMAR, then the Test lens will be statistically non-inferior to the Control lens.

Photopic monocular uncorrected near visual acuity (UNVA) at 40 cm at Post-Operative Visit 4 (Day 120 to Day 180 after second eye IOL implantation) will be summarized using continuous summary statistics in logMAR units by treatment assignment for the first implanted eyes of ITT Set Subjects. Missing data will be imputed using the Markov chain Monte Carlo (MCMC) multiple imputation method. After imputation of missing data, the statistical hypotheses will be tested using two-sided two-sample t-tests by imputation. An overall p-value resulting from the multiple imputation method will be estimated. The treatment effect (mean Test group IOL VA minus mean Control group IOL VA) in logMAR units will be summarized using continuous summary statistics and a two-sided 95% confidence interval. If the p-value from the multiple imputation analysis is less than or equal to 0.05 and the treatment effect is less than zero (i.e., the Test lens mean logMAR VA is superior to the mean for the control), then it will be concluded that the Test IOL is statistically successful (i.e., superior to the Control IOL) in this outcome.

Photopic monocular uncorrected intermediate visual acuity (UIVA) at 66 cm in first implanted eyes will be summarized and analyzed using the methods described for UNVA.

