### 11.4.4.2 Change from Baseline in Photopic Monocular UNVA

Photopic monocular uncorrected near visual acuity (UNVA) at 40 cm at Baseline, at Post-Operative Visit 4 (Day 120 to 180 after second eye IOL implantation), and the Change from Baseline to Visit 4 will be summarized using continuous summary statistics in logMAR units

by treatment assignment for the first implanted eyes of ITT Set Subjects. A paired t-test will be used to test the statistical hypothesis for the Test lens group.

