# 15 APPENDICES

# Appendix A STUDY FLOW CHART

Examination	Pre-Op 0A/B (Both Eyes)	Operative 00A (1st Eye)	Post-Op 1A (1st Eye)  Day 1 to 2	Post-Op 2A a (1st Eye)  Day 7 to	Post-Op 3A (1st Eye)	Operative 00B (2 nd Eye)	Post-Op 1B (2 nd Eye)	Post-Op 2B (2 nd Eye)	Post-Op 3B (2 nd Eye)	Post-Op 4 (Both Eyes)
	to -5	Day 0	Day 1 to 2	14	to 60	to 30	2 Post Visit 00B	14	60 Post Visit 00B	to Day 180 Post Visit 00B
Informed Consent	X									
Demographics	X									
Ocular and Non-Ocular Medical History	X									
Inclusion/Exclusion	X	X b				X b				
Patient Reported Outcome Questionnaires	X									X
Potential Visual Acuity	X									
Corneal Topography	X									
Targeted Refraction / IOL Power Calculation / Axial Length Determination/Anterior Chamber Depth	X									
Chord length μ	X									X
Keratometry	X				X				X	X

15 April 2021, Version 5.0 CONFIDENTIAL Page **67** of **88** 

[figure not shown]
Examination	Pre-Op 0A/B (Both Eyes)	Operative 00A (1st Eye)	Post-Op 1A (1st Eye)	Post-Op 2A a (1st Eye)	Post-Op 3A (1st Eye)	Operative 00B (2 nd Eye)	Post-Op 1B (2 nd Eye)	Post-Op 2B (2 nd Eye)	Post-Op 3B (2 nd Eye)	Post-Op 4 (Both Eyes)
	Day -30 to -5	Day 0	Day 1 to 2	Day 7 to 14	Day 30 to 60	Day 7 to 30	Day 1 to 2 Post Visit 00B	Day 7 to 14 Post Visit 00B	Day 30 to 60 Post Visit 00B	Day 120 to Day 180 Post Visit 00B
Manifest Refraction (ETDRS)	X			X	X			X	X	X
Randomization	Xe									
Operative Procedures		X				X				
Photopic Pupil Size	X								$X^{\mathbf{d}}$	X
Mesopic Pupil Size	X									X
UDVA – photopic, monocular	X				X				X	X
CDVA – photopic, monocular	X			X	X			X	X	X
UNVA f – photopic, monocular	X				X				X	X
DCNVA f – photopic, monocular	X				X				X	X
UIVA g – photopic, monocular	X				X				X	X
DCIVA g – photopic, monocular	X				X				X	X
UNVA f – photopic, binocular									X	X
UIVA g – photopic, binocular									X	X
UNVA f – mesopic, binocular	X				X				X	X
UIVA g – mesopic, binocular	X				X				X	X

[figure not shown]
Examination	Pre-Op 0A/B (Both Eyes)	Operative 00A (1st Eye)	Post-Op 1A (1st Eye)	Post-Op 2A a (1st Eye)	Post-Op 3A (1st Eye)	Operative 00B (2 nd Eye)	Post-Op 1B (2 nd Eye)	Post-Op 2B (2 nd Eye)	Post-Op 3B (2 nd Eye)	Post-Op 4 (Both Eyes)

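### The three primary acuity models leave out the scheduled preoperative value of the same acuity; prespecifying it would be a small, nearly cost-free gain in precision

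*Combined protocol and SAP*

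**What the plan says.** All three primary performance endpoints are photopic monocular acuities of the first implanted eye (eye A) at Visit 4.

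- **UDVA (11.4.3.1):** the treatment difference is estimated in the Per Protocol Set "using a statistical model with treatment and site as fixed factors". Missing values are not imputed.
- **UNVA (11.4.3.2):** in the ITT Set, after MCMC multiple imputation, the hypotheses are tested with "statistical models with treatment and site as fixed factors by imputation". The variables in the imputation model are not listed.
- **UIVA (11.4.3.3):** this endpoint "will be summarized and analyzed using the methods described for UNVA".
- **Synopsis, Primary Performance Analyses:** for UNVA, "the statistical hypotheses will be tested using two-sided two-sample t-tests by imputation", and UIVA follows the same method. This version has no site term and no baseline term.

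The Appendix A flow chart has a row for "UDVA – photopic, monocular" and matching rows for UNVA and UIVA. All three are marked at the Preoperative Visit for both eyes, and again at Visit 3A for the first eye. Section 11.4.4.2 already uses the preoperative value, summarizing "Photopic monocular uncorrected near visual acuity (UNVA) at 40 cm at Baseline" together with Visit 4 and the change between them; 11.4.4.3 does the same for UIVA. Section 11.4 leaves further detail to a SAP to be approved before database lock.

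**The concern.** A baseline measure of the outcome itself is the usual first candidate for a covariate in a between-arm comparison. Here it is scheduled for everyone and already feeds two secondary endpoints, but the primary comparisons do not use it and the plan does not say why.

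Two things are at stake. One is precision: with about 50 Control subjects, chance differences in preoperative acuity between the arms go uncorrected, and any variance that preoperative acuity explains stays in the error term. The other concerns UNVA and UIVA only. Multiple imputation is only as credible as the variables it conditions on, and the plan does not name them. It allows for losses of up to 10%, which is up to 168 − 150 = 18 subjects.

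**Working it through.** **Inputs.** From 11.2.1: 100 Test and 50 Control subjects, common SD 0.15 logMAR, difference (UNVA, UIVA) or non-inferiority margin (UDVA) of 0.2. From the Synopsis: up to about 12 sites, taken here as 12. The correlation r between preoperative and Visit 4 acuity is not given, so 0 to 0.3 is assumed.

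**1. The plan's own power.**

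SE = 0.15 × √(1/100 + 1/50) = 0.15 × √0.03 = 0.0260, and 0.2 / 0.0260 = 7.70.

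- UNVA and UIVA, two-sided 0.05: Φ(7.70 − 1.96) = Φ(5.74), above 99.99%.
- UDVA, one-sided 0.05: Φ(7.70 − 1.645) = Φ(6.05), above 99.99%.

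Both reproduce the stated figure of more than 99%.

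**2. Effect of the covariate on the standard error.** With a known slope, the SE is multiplied by √(1 − r²). Estimating the slope inflates the variance on average by about 1/(150 − 13 − 2) = 1/135, where 13 counts the intercept, treatment and 11 site terms. That multiplies the SE by √(1 + 1/135) = 1.0037.

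| Assumed r | √(1 − r²) | SE change, slope cost ignored | Net factor (× 1.0037) | Net SE change |
|---|---|---|---|---|
| 0 | 1.000 | 0 | 1.004 | +0.4% |
| 0.1 | 0.995 | −0.5% | 0.999 | −0.1% |
| 0.2 | 0.980 | −2.0% | 0.983 | −1.7% |
| 0.3 | 0.954 | −4.6% | 0.957 | −4.3% |

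Break-even is where (1 − r²)(1 + 1/135) = 1, so r² = 1/136 and r is about 0.09.

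On the logMAR scale, ignoring the slope cost, the 95% half-width is 0.0513 unadjusted, 0.0503 at r = 0.2 and 0.0490 at r = 0.3.

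**3. Chance imbalance.** The difference in mean preoperative acuity between arms has a standard error of √0.03 = 0.173 baseline SDs. A gap of 1.96 × 0.173 = 0.34 SD is therefore within ordinary chance. It shifts the unadjusted estimate by r × 0.34 × 0.15: about 0.005 logMAR at r = 0.1, 0.010 at 0.2 and 0.015 at 0.3. These shifts are small beside the 0.2 margin or difference.

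**4. If the planning values are too optimistic.** With SD 0.30, or with a true difference of 0.1 and SD 0.15, superiority power is 96.9% unadjusted, 97.4% at r = 0.2 and 98.0% at r = 0.3. These figures charge one degree of freedom for the covariate and leave out the site terms.

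**5. Imputation.** Section 11.4.3.2 names the method but no variables, so the text neither includes nor excludes preoperative acuity. Visit 3A acuity of the same eye is measured after the lens is in place and is probably the stronger predictor of Visit 4. UDVA is not imputed, so this step does not concern it.

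**The case against.** The strongest reply is that nothing here is an error. Randomization is stratified by site and site is in the model, so the test and the estimate are valid, and chance imbalance is already covered by the stated error rates. That stands. A reader might infer that omitting baseline biases the primary comparison; the documents give no support for this.

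The second reply is that the gain may be close to nothing. Section 11.1.2.2.2 describes the preoperative value as that of a cataractous eye with its own refractive error. Surgery removes the cataract and replaces the lens, so the correlation may well be low. This also stands. A reader might look to a value such as r = 0.5, where the SE would fall by about 13%, but nothing in the documents points to it. Nor does adjustment help at every correlation: below about 0.09 it costs slightly more than it returns.

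Third, adjustment can lose data. The acuity is scheduled for every subject, which does not guarantee that it is recorded. The Per Protocol rules in 11.4.7 require Visit 4 values but not a baseline value, so a subject without preoperative UDVA would drop out of an adjusted complete-case model. This stands, and the fix needs a rule for it.

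Finally, a reader might infer that the plan shuts preoperative acuity out of the imputation. The variables are simply unlisted, and further detail is deferred to the SAP, so only the lack of specification can be asserted.

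**Conclusion.** The point holds as a minor, optional improvement. All three primary models omit the preoperative value of the same acuity, although it is scheduled for every subject. Over assumed correlations of 0 to 0.3, the net effect on the standard error runs from a 0.4% increase to a reduction of about 4%. This rests on the plan's SD and sample sizes, on 12 sites, and on a correlation that the documents do not give.

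The tempting stronger conclusion, that the omission puts the primary results at risk, is not supported. Power is above 99% under the plan's assumptions with or without the covariate, and about 97% without it even if the SD is doubled. For UNVA and UIVA the imputation model is under-specified, which is a separate and equally modest matter.

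**What to change.** 1. In 11.4.3.1 to 11.4.3.3 and in the SAP, add the preoperative value of the same acuity in eye A as a prespecified covariate to each treatment-plus-site model.
2. State a simple rule for a missing baseline, for example imputing the covariate by its overall mean, so that no subject is dropped on that account.
3. For UNVA and UIVA only, list the variables of the MCMC imputation model: treatment, site, and the preoperative and Visit 3A values of the same acuity.
4. While editing, bring the Synopsis t-tests into line with the models in Section 11.

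The cost is a few sentences and one degree of freedom per model. No new data are needed. The change should be made before unmasking, because a covariate added later could look selective.
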